Study Design: We propose a prospective, randomized, trial of oral DHA supplementation of lactating mothers. Cincinnati Children's Hospital research staff will screen all infants admitted to the Cincinnati University Hospital NICU on a weekly basis. Eligible participants will be identified by the Principle Investigator and the research coordinator. Potential participants (mothers) will be approached regarding the possibility of study participation by study staff trained in the consent process. Eligible participants will be screened and if eligible and interested, will be consented within one week of being admitted to Cincinnati University Hospital NICU. Maternal consent will be obtained for the infant. Consent will be administered by Cincinnati Children's Hospital Medical Center staff trained in the consent process and having completed all required CITI training. Informed consent will be documented by an Informed Consent Process Note. All data and infants biological sample collection will take place during the infants stay in Cincinnati University Hospital NICU. Mother's biological samples will be collected by Cincinnati University Hospital NICU. Study staff and Hoxworth outpatient lab.

After informed consent, lactating mothers will be randomized by The Cincinnati University Hospital Investigational Pharmacy to receive DHA (DHA- Martek Biosciences, now known as DSM Nutritional Lipid- Expecta®) 200 mg, or 1000 mg/day. The randomization schedule has been devised in collaboration with the Biostatistics expert, [name], identified in these studies. We have used the Consolidated Standards of Reporting Trials (CONSORT)framework [33].

Participants who meet any exclusion criteria during the course of the study, are non-compliant or are lost to follow-up will be withdrawn. Provided that there are at least 8 mother/baby pairs with evaluable data in each group, withdrawn participants will not be replaced. Anticipated enrollment will take two years.

Inclusion criteria: Lactating mothers at Cincinnati University Hospital with infants born at <29 weeks gestation admitted to The Cincinnati University Hospital NICU

Exclusion criteria:

- Infants with the presence of congenital anomalies (trisomy 13, 18, 21, urethral, gastrointestinal and cardiac defects) that affect the standard course of care.
- mother's <18 and
- mothers with known allergy to algeal source

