An additional teaspoon of fresh milk will be collected at Week 4 and aliquoted into whole, aqueous, and fat layer fractions. Fat layer RNA will be isolated using a MaxwellTM 16 integrated system (Promega, Madison, WI). RNA quantity (target=1000 ng) and quality (A260:A280 target \geq 1.9) will be confirmed prior to RNA sequencing. Na:K ratio, as a marker of mammary gland inflammation, will be assayed on the milk aqueous fraction.

All biological samples will be collected within study time frames as feasible.

Stool will also have bacteria and yeast measured by using 16S ribosomal markers. **Growth and Hospitalization**

Growth measures are standard of care at University NICU and include weekly weight, length, and head circumference measurements and will be extracted from the participant's charts. At discharge we will obtain body composition on the infant using a validated isolette that has non-invasive, volume and mass measurement capability. Cincinnati University Hospital course records that could be pertinent to the study outcomes will be collected from both mother and infant. Compliance will be assessed as part of diet record evaluations; rate of compliance will not be assessed

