Statistical Plan: All data analyses will employ intention to treat principles. In our primary analysis, ANOVA will be used to compare DHA levels at four weeks in the breast milk of mothers assigned to the different concentrations of DHA supplements. As in any prospective study, If we experience substantial loss to follow-up (e.g., > 10% of subjects), we will fit a linear mixed model [35] We will use two sample t tests to compare infant blood DHA concentrations and TNF-alpha and IL-10 levels at 8 weeks of infants randomized to DHA-supplemented milk. The comparison of DHA concentrations will be performed at a significance level of 0.05 while the comparison of TNF-alpha and IL-10 levels will be performed at a significance level of 0.025 to adjust for the two outcomes. All analyses will be performed using SAS (SAS Inc., Cary, NC). Our sample size determination to detect a two-fold difference in the DHA levels at four weeks in expressed milk of mothers assigned DHA treatments, we will need data on a total of 16 mothers at week 4 (8 per group). This sample size calculation was based on 90% power, a two-sided significance level of 0.025, and a coefficient of variation (CV) of 30%; the CV is based on a previous study [36]. Assuming a conservative 20% loss to follow-up before week 4, we will enroll enough mother-infant pairs to achieve our desired sample size of 16 at 4 weeks. It is expected that evaluable data at week 4 from at least sixteen of the mother/baby pairs (8 pairs per group) will be obtained. The University Hospital Investigational Pharmacy will randomize participants per the Consolidated Standards of Reporting Trials (CONSORT) framework. Secondary outcomes will use linear mixed models and Bonferroni correction.

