Among participants with adequate quality milk fat layer RNA at Week 4, five pairs will be randomly selected from each group for sequencing (matched on gestational week of delivery, milk DHA concentration at baseline, and Week 4 breast milk output level (exceeds, at, or below infant's needs). The remaining will be set aside for future studies. RNA integrity (RIN \geq 7) will be confirmed at the microarray core and then sent to the gene discovery core for RNA-Seq library preparation (Illumina TruSeq RNA kit) and sequencing (Illumina Hi-Seq2500). Libraries will be multiplexed in batches of 10 with at least 30 million 150bp paired-end reads per sample. Sequence reads will be trimmed for quality and then aligned to the human genome using TopHat. We will use Cufflinks to determine gene expression levels, normalized to Fragments Per Kilobase of transcript per Million mapped reads (fpkm). We will identify differentially expressed genes using DESeq and intersect this gene list with known cytokine signaling genes. We will also conduct Gene Set Enrichment Analysis. Significant biomarker genes will be assayed for all participants using TaqManTM qPCR. Power: N=5 pairs per group enables 90% power (α =0.05) to detect 1.5-fold differences between DHA versus placebo for moderate to high abundance genes (FPKM \geq 10) and 3.0-fold differences for low abundance genes (FPKM \sim 1.0).

[name] PhD.,

The University of Cincinnati / Cincinnati Children's Hospital Medical Center, Docosahexaenoic Acid Supplementation to Mothers to Improve Preterm Infant Nutrition and Immune Homeostasis

July 12, 2013

Safety: All records will be kept according to IRB and regulatory standards. All PHI will be stored in a password protected database. All biological sample data will be kept in a separate database from PHI and study identifiers. Written research records, participant contact information, and signed consent forms will be kept in a locked file cabinet near the study coordinator's work station. All data will be entered from source documents into a Redcap database using a password protected, secure server. Individually identifiable information will not be included in the data set or in any reports.

Laboratory samples will be de-identified and stored at Cincinnati Children's Hospital Medical Center and Nationwide Children's in Columbus Ohio.

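### Matching the RNA-Seq subsample on Week 4 milk output conditions a randomised comparison on a post-treatment variable and can hide part of the dose effect

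*Combined protocol and SAP*

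**What the plan says.** The RNA paragraph of the Statistical Plan first restricts the pool: "Among participants with adequate quality milk fat layer RNA at Week 4". From that pool, "five pairs will be randomly selected from each group for sequencing (matched on gestational week of delivery", and the matching list continues with "milk DHA concentration at baseline, and Week 4 breast milk output level". Output has three levels: "exceeds, at, or below infant's needs".

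The sequenced groups are compared with DESeq, and the resulting gene list is intersected with known cytokine signalling genes. Genes found significant are then measured by qPCR in all participants.

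Study Procedures and the Figure 3 time table place breast expression data at Week 4 only. The RNA comes from the Week 4 milk too, and in that same milk "Na:K ratio, as a marker of mammary gland inflammation, will be assayed on the milk aqueous fraction". Aim 2 (Purpose) expects the higher intake to lower pro-inflammatory cytokine expression in plasma and milk.

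The expected pool is "evaluable data at week 4 from at least sixteen of the mother/baby pairs (8 pairs per group"). The plan states no tolerance for the matching, no categories for baseline DHA, no fallback, and no term for matching in the DESeq analysis. It also does not say whether matching is one-to-one across arms or a balance of groups.

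**The concern.** Gestational week and baseline milk DHA are fixed before the supplement can act, so balancing the arms on them is harmless. Week 4 output is not fixed. It is observed after about four weeks of treatment, together with the outcome.

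The protocol treats mammary inflammation as relevant to this milk sample, since it measures a marker of it there. Suppose inflammation lowers output and the higher dose lowers inflammation. Output would then carry part of the dose effect. Choosing mothers so that the arms have equal output would favour relatively more inflamed mothers in the 1000 mg arm and relatively less inflamed mothers in the 200 mg arm, and the contrast in cytokine genes would shrink because of the selection.

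What is at stake is the screen. It decides which genes reach qPCR, so a gene whose dose effect has been selected away is never tested in the full randomised sample. The general commitment to intention to treat in the Statistical Plan does not protect a subsample chosen on a post-treatment variable.

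**Working it through.** **1. The pool.** The plan says "we will need data on a total of 16 mothers at week 4 (8 per group"). Its inputs are 90% power, two-sided 0.025, CV 30% and a two-fold difference. Take means 1 and 2 with SDs 0.30 and 0.60. The pooled SD is √((0.30² + 0.60²)/2) = 0.474, and the standardised difference is 1/0.474 = 2.11. The noncentral t gives power 89.9% at 7 per group and 94.3% at 8, so 8 per group reproduces. Five of about eight dyads per arm would be sequenced. The separate RNA-Seq power statement gives no dispersion and cannot be checked.

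**2. When each selection variable is fixed.**

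| Variable | Timing |
|---|---|
| Gestational week | at birth, before randomisation |
| Baseline milk DHA | at start of supplementation |
| Milk output level | Week 4, with the RNA outcome |
| RNA quality | Week 4, a property of the outcome sample |

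**3. Illustration A: output responds to inflammation.** All inputs are assumed; none is in the documents. The true dose effect on inflammation is −0.8 SD. Output = −r × inflammation + independent noise, scaled to unit variance. Arms are matched on pooled thirds of output, to mimic the three levels (400,000 simulated mothers per arm). The implied dose effect on output is 0.8 × r.

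| r | Effect on output (SD) | Effect left after matching (SD) | Loss |
|---|---|---|---|
| 0.3 | 0.24 | 0.742 | (0.8 − 0.742)/0.8 = 7% |
| 0.5 | 0.40 | 0.642 | (0.8 − 0.642)/0.8 = 20% |
| 0.7 | 0.56 | 0.479 | (0.8 − 0.479)/0.8 = 40% |

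**4. Illustration B: output lies on the path to expression.** Total effect = direct effect + shift in output × slope of expression on output, with the direct effect set at 0.5 SD. For a shift of 0.5 and a slope of 0.3 the total is 0.5 + 0.15 = 0.65, and the matched contrast is 0.531, or 82% kept. Over slopes 0.3 to 0.6, a 0.5 SD shift keeps 82% to 70% and a 1 SD shift keeps 72% to 59%. Adding an unmeasured common cause of output and expression lowers these to 67% to 58% and 48% to 42%.

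**5. The null case.** If the dose does not shift output, the matched contrast equals the total effect (ratio 1.00) in every variant of B, even when output and expression are related.

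**6. Feasibility of the matching.** Exact one-to-one matching across arms was simulated with 8 per arm, five equally likely gestational weeks and three equally likely output levels. It yields 2.8 pairs on average and at least five in 8% of runs. Adding baseline DHA as high/low gives 0.6%. Dropping output but keeping week and high/low DHA gives only 23%; with six week classes (23 to 28) this is 15%, or 3% with DHA in thirds. Allowing one week's difference, with six week classes and high/low DHA, gives 12–20% with output and 78% without. Under group balance (mean gestation within 0.5 week, mean baseline DHA within 0.3 SD), suitable sets of five per arm exist in about 70–73% of trials with identical output counts and 88–90% with counts within one. These figures assume that all RNA is adequate; the plan gives no pass rate.

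**The case against.** **The size is assumed.** No passage says that DHA changes output or that mammary inflammation lowers it. The output category is relative to the infant's needs, so it also varies with the infant. This stands: the 7–40% range is an illustration, and it would go too far to say that the selection does pick unusually inflamed high-dose mothers.

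**The effect is small beside the noise.** With five per arm the standard error of a difference is √(2/5) = 0.63 SD. Power for 0.8 SD at two-sided 0.05 is 20% unmatched, against 18%, 15% and 10% after the three losses above. This stands for a single gene of that size. It is still no reason to add a systematic loss to a comparison with so little power.

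**The rest of Aim 2 is untouched.** Cytokines in milk and blood are assayed outside this subsample, and hits are checked by qPCR in everyone. This limits the damage to the gene screen, but qPCR cannot bring back genes that the screen missed.

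**Matching on output may reduce noise.** That is plausible, though the plan gives no reason for the factor. Any gain would come at the price of a contrast that no longer estimates the total dose effect.

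**A reader might infer that five matched pairs are almost impossible to find.** The documents do not support this. Five pairs are taken from each group, and the sample-size text uses pairs for mother and baby, so five dyads per arm is the natural reading. No exact cross-arm rule is stated. Under such a rule, matching would usually fail without output too. Nor do the documents show that matching would be relaxed with Week 4 milk DHA in hand, since they give no assay timing relative to selection.

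**Conclusion.** The point holds as a design weakness in a secondary, mechanistic analysis, and it should be corrected before the subsample is drawn. Week 4 milk output is a post-randomisation variable, and matching on it can remove or distort part of the dose effect on milk cytokine genes.

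The direction and size depend on links that the documents do not state. With a true 0.8 SD effect the loss is 7% to 40% for assumed correlations of 0.3 to 0.7 in absolute value. It is nil if the supplement leaves output unchanged. If an effect through output ran against the direct effect, matching could overstate the total instead.

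The conclusion does not rest on a shortage of matched mothers, which would follow only from a strict one-to-one rule that the protocol does not contain. The RNA quality filter is also applied after randomisation, but sequencing needs usable RNA, whereas the output factor is optional.

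**What to change.** In the RNA paragraph of the Statistical Plan:

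- Delete Week 4 milk output from the matching factors.
- State that five mother/baby dyads per arm are selected at random within arm, balanced only on pre-dose variables: gestational week first, then nearest baseline milk DHA. This also settles how the selection can be both random and matched. With eight usable dyads per arm there are 56 × 56 = 3,136 possible selections (8!/(5!·3!) = 56 per arm), so one can be drawn at random from the best balanced.
- Report Week 4 output and Na:K by arm for the sequenced mothers descriptively. Label any output-adjusted comparison as a sensitivity analysis.
- Report by arm how many samples failed the RNA quality check.

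The cost is a few sentences, with no extra samples or assays. The downside is small: output may differ between the sequenced groups and add some variance.

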Study Design: Breast milk providers for enterally-fed preterm infants <29 weeks gestational age will be randomized to receive daily oral supplementation with DHA at 200mg or 1000mg. Based on our previous study with a placebo, it was apparent that even motivated mothers had a paucity of DHA in the diet and in their prenatal supplement therefore we felt it important to randomize to at least the baseline 200mg per day and then added the other dose as the target optimal dose for milk concentrations to achieve 0.8 mol weight percent. This concentration of DHA would provide intrauterine accretion when fed at 150ml/kg per day in the NICU. DHA concentration will be analyzed by gas chromatography in milk and infant cell membranes. Milk and infant plasma cytokine levels and cytokine production capacity will be measured. All samples will be obtained at baseline (within first week of life), weeks 2, 4, and 8. Inflammatory complications (BPD, NEC, and ROP) will be tracked. Cytokine gene expression from RNA extracted from the Week 4 milk samples will also be examined. Stool samples will not only have fatty acids but also bacteria and yeast analyzed.

Significance: Our unique investigation of maternal supplementation to improve DHA delivery to preterm infants represents the first study of its kind.

Purpose

The objective of this project is to improve preterm infant intake of DHA that approximate the levels obtained by fetal accretion during the third trimester of pregnancy and determine if there are functional relationships to inflammation, growth, and development.

The following specific aims will test the hypotheses that:

Aim 1: Maternal DHA supplementation will improve plasma and milk DHA concentration in the mother and preterm infant

Aim 2: Higher intakes of dietary DHA will decrease expression of pro-inflammatory cytokines and increase expression of anti-inflammatory cytokines in the plasma and milk samples of

breast feeding mother - infant dyads through the alteration of sRAGE signaling. This will result in an improved microbiome as evidence of bacteria and yeast in stool samples.

Background:

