All supplements will be stored in the Investigational pharmacy at Cincinnati University Hospital. FDA Investigator IND was accepted and in addition regards DHA as a generally regarded as safe (GRAS) category with levels < 3 grams per day in the adult diet. Our supplement strategy is well below this level.

Risk/Benefit Analysis: The risk is very negligible since the product has been on the market and women have been taking up to 3 grams per day without adverse effects in cardiovascular prevention trials. The benefit is great to the pregnant and lactating woman to improve health.

Collaboration: [name] will collaborate with the original author of this work [name] MD, MS, RD who is now at Mead Johnson Nutrition to complete and write the manuscript. [name] will provide medical oversight as a Sub-Investigator. [name] will collaborate in collecting the lactation history data and capturing mammary cell RNA from the milk fat layer and conducting transcriptome analysis on the RNA-sequenced samples.

Potential Risks, Discomforts, Inconveniences and Precautions

Minimal pain or bruising may occur at the blood draw site. This occurrence is minimized by having blood drawn by trained and experienced nurses and phlebotomists. All infant blood will be drawn during standard of care routine nutritional labs therefore eliminating an additional venipuncture.

Because of the longevity of the product on the market and its use in infant formulas we do not anticipate any unknown or unforeseeable risks associated with this study.

The mothers are sent home with an AE form to collect any adverse events that occur from their first dose of the investigational agent until the end of the study. This form will be checked at all study time points by study staff.

Since infants in this study are premature, it is anticipated that adverse changes in clinical status will occur related to their prematurity. The following common, serious neonatal morbidities as defined in the NRN Generic Data Base (GDB) will also be collected. These include data on inhospital growth, the incidence and severity of intraventricular hemorrhage, seizures, patent ductus arteriosus (PDA) and its treatment, nosocomial sepsis (and organisms), hearing impairment, and pneumothorax.

[name] PhD.,

The University of Cincinnati / Cincinnati Children's Hospital Medical Center,

Docosahexaenoic Acid Supplementation to Mothers to Improve Preterm Infant Nutrition and Immune Homeostasis

July 12, 2013

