Maternal blood – fatty acids Diet analysis Buccal swabs (saliva) Infant blood - fatty acids, cytokines, and sRAGE Nutrition labs Growth measures: Weight, length, head circumference Diet analysis Stool from diaper Buccal swabs (saliva)	Infant blood - fatty acids and cytokines labs, sRAGE Stool from diaper Buccal swabs (saliva) Growth measures	Maternal blood – fatty acids Diet analysis Exercise and Smoking habits Breast milk expression and breastfeeding patterns and concerns Anthropometry (weight, height and circumferences) Buccal swabs (saliva) Infant blood fatty acids and cytokines labs, sRAGE Stool from diaper Buccal swabs (saliva) Growth measures	Buccal swabs (saliva) Infant blood - fatty acids and cytokines labs, sRAGE Buccal swabs (saliva) Stool from diaper Growth measures Body composition using the Pea Pod ® air displacement isolette

Figure 3. Study	time table for r	recruitment, samp	ole, and data collection

Summary and Significance:

Premature birth is responsible for 75% of perinatal death [37]. Inflammatory conditions such as necrotizing enterocolitis (NEC), bronchopulmonary dysplasia (BPD), and retinopathy of prematurity (ROP) in the preterm infant are a tremendous source of morbidity and mortality. DHA is a key regulator of inflammation. Breast milk is the ideal delivery vehicle for DHA based upon the ability of the breast to provide balanced fatty acid composition as well as anti-infective molecules. Further understanding of the mechanisms could ensure our nutritional strategy is optimal.

References:

- 1. Fanaroff, A.A., et al., *Trends in neonatal morbidity and mortality for very low birthweight infants*. Am J Obstet Gynecol, 2007. **196**(2): p. 147 e1-8.
- Innis, S.M., Essential Fatty Acid Transfer & Fetal Development. Placenta, 2005. Suppl A: p. S70-75.
- 3. Turner, N., P.L. Else, and A.J. Hulbert, *Docosahexaenoic acid (DHA) content of membranes determines molecular activity of the sodium pump: implications for disease states and metabolism.* Naturwissenschaften, 2003. **90**(11): p. 521-3.
- 4. SanGiovanni, J.P., et al., *Meta-analysis of dietary essential fatty acids and long-chain polyunsaturated fatty acids as they relate to visual resolution acuity in healthy preterm infants.* Pediatrics, 2000. **105**(6): p. 1292-8.
- 5. Innis, S.M., *Perinatal biochemistry and physiology of long-chain polyunsaturated fatty acids*. J Pediatr, 2003. **143**(4 Suppl): p. S1-8.

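### No gestational age or baseline size term is pre-specified for infant growth and body composition, although infants enter at any gestational age below 29 weeks and there are about 8 per arm

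*Combined protocol and SAP*

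**What the plan says.** The Purpose section sets out, besides raising DHA intake, to "determine if there are functional relationships to inflammation, growth, and development". Under Study Design, the inclusion criterion sets an upper limit of 29 weeks' gestation and no lower limit.

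Under Growth and Hospitalization, weight, length and head circumference come from the charts, where they are recorded every week, and body composition is measured once, at discharge. Figure 3 repeats the growth measures at baseline and weeks 2, 4 and 8, and lists "Growth measures Body composition using the Pea Pod ® air displacement isolette" in a column headed both week 8 and discharge.

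The Statistical Plan gives growth and body composition no model of their own. The only sentence that can apply is "Secondary outcomes will use linear mixed models and Bonferroni correction". It lists no covariates. Neither Study Design nor the Statistical Plan names a stratification factor for the randomisation.

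Gestational age enters an analysis step once: the RNA-sequencing subsample is "matched on gestational week of delivery" and two other factors. The risk section adds "Since infants in this study are premature, it is anticipated that adverse changes in clinical status will occur related to their prematurity", and includes in-hospital growth among the data collected in that connection.

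**The concern.** Two infants at the same study week can differ in maturity by the whole spread of gestational age at entry, and maturity is a plausible driver of size. The design as written does not balance the arms on gestational age, and the analysis as written does not adjust for it. With so few infants, a difference in growth between arms could partly reflect a difference in maturity, or a real difference could be masked by one.

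Leaving the covariates open also means they could be chosen after the data are seen. With about 16 infants that choice could change the growth conclusion. Gestational age is known for every infant before randomisation because eligibility depends on it, so nothing prevents the choice from being fixed now.

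**Working it through.** **The plan's own sample size.** The Statistical Plan describes "Our sample size determination to detect a two-fold difference in the DHA levels at four weeks in expressed milk", for which "we will need data on a total of 16 mothers at week 4 (8 per group"). The basis is "This sample size calculation was based on 90% power, a two-sided significance level of 0.025, and a coefficient of variation (CV) of 30" per cent. Take means of 1 and 2 with a CV of 30% in each arm. The SDs are then 0.3 and 0.6, and the average-variance SD is √((0.09 + 0.36)/2) = 0.474. A two-sample t calculation at two-sided 0.025 gives power of 89.9% with 7 per group and 94.3% with 8, so 8 per group is reproduced. This sizing concerns milk DHA only. No power is stated for growth or body composition.

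**Inputs for the growth question.** N = 16, 8 per arm (Statistical Plan). The correlation r between gestational age and the outcome is not in the documents; 0 to 0.7 is an assumed range.

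**Chance imbalance.** In SD units of gestational age, the standard error of the difference in arm means is √(2/8) = 0.50.
- P(difference above 0.5 SD) = 2 × P(Z > 1) = about 32%.
- P(difference above 1 SD) = 2 × P(Z > 2) = about 5%.

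An imbalance of 0.5 SD moves an unadjusted outcome difference by 0.5 × r outcome SDs: 0.15 at r = 0.3, 0.25 at r = 0.5 and 0.35 at r = 0.7. Larger imbalances move it further.

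**Precision with one covariate.** The expected variance ratio, adjusted to unadjusted, is (1 − r²) × (1 + 1/(N − 4)) = (1 − r²) × 13/12.

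| r | Variance ratio | Power for a 1 SD difference |
|---|---|---|
| unadjusted | 1 | 46% |
| 0 | 1.08 | 43% |
| 0.3 | 0.99 | 46% |
| 0.5 | 0.81 | 54% |
| 0.7 | 0.55 | 70% |

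Break-even is r = √(1 − 12/13) = 0.28. Power is for a single-time comparison at two-sided 0.05 before any Bonferroni correction (14 residual degrees of freedom unadjusted, 13 adjusted). If four growth endpoints shared the error rate (an assumed number; 0.05/4 = 0.0125), power for 1 SD would be 24% unadjusted, 30% at r = 0.5 and 45% at r = 0.7.

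**Precision with two covariates.** The penalty becomes 1 + 2/(N − 5) = 13/11 = 1.18. Break-even is R² = 1 − 11/13 = 0.154, a multiple R of about 0.39.

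**Gestational age added to baseline size.** What counts here is the partial correlation p given baseline. Adding the second covariate multiplies the variance by (1 − p²) × (13/11)/(13/12) = (1 − p²) × 12/11, so break-even is p = √(1/12) = 0.29. As an illustration with assumed correlations of 0.6 (gestational age with outcome), 0.7 (gestational age with baseline) and 0.7 (baseline with outcome), p = (0.6 − 0.49)/0.51 = 0.22. The variance then rises by about 4%.

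**The case against.** The strongest reply is that the plan is silent and does not exclude gestational age. A reader might infer from Figure 3 that growth and body composition will be compared between arms with no adjustment. The documents do not say that. The Figure 3 entry is a data-collection item, neither aim names growth as an outcome, and the mixed-model sentence lists no covariates of any kind. The between-arm test is itself inferred from the objective and that sentence. This stands, and it sets the form of the point: the covariates are not pre-specified.

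A reader might also infer that adjustment is a free gain, or that maturity dominates the variance of size and fat mass. Neither is supported. Adjustment costs variance at N = 16 unless the correlations exceed the break-even values above, and the documents give no correlation. Gestational age would explain more than half the variance only if r exceeded about 0.71. The RNA matching concerns maternal milk samples and the risk statement concerns clinical status, so neither shows that the protocol regards gestational age as prognostic for growth.

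Three further limits stand. For weight, length and head circumference, a mixed model can already use the baseline measurements, so the comparison with an unadjusted t-test overstates what gestational age would add. For body composition, the fixed-week argument does not carry over, because measurement at discharge lets age at measurement vary as well. A reader might also infer that the growth analysis is confined to the four Figure 3 visits. It is not: weekly chart values are already to be extracted, and nothing restricts the analysis to four visits.

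None of this supplies the missing terms or lowers the chance of imbalance.

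**Conclusion.** The point holds as a gap in pre-specification with a cheap remedy. Gestational age is controlled neither by a named stratification factor nor by a stated model term, and baseline size is not named as a covariate either. The 32% imbalance figure rests on simple randomisation with 8 infants per arm and a normal approximation. The resulting shift and any gain in precision depend on correlations that must be assumed.

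The case for adjustment rests at least as much on protection against imbalance, and on fixing the model in advance, as on precision. For the serial measures, the precision gain from gestational age may be small once baseline size is in the model. Body composition has no baseline, so gestational age is the natural covariate there, but its correlation with a measurement taken at discharge is unknown. Growth was not what the trial was sized for, and even a well-chosen covariate leaves modest power. The primary week 4 milk DHA comparison and its 16 evaluable mothers are unaffected.

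**What to change.** Add to the Statistical Plan:
- For weight, length and head circumference, the mixed models will include the baseline value of the same measure and gestational age at birth, continuous in weeks.
- For body composition, the model will include gestational age at birth, and age at measurement will be reported by arm. The timing in Growth and Hospitalization (discharge) and in Figure 3 (week 8 or discharge) should be reconciled.

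Gestational age is known at entry and the baseline measures are already scheduled; age at measurement needs only the date of the body composition test. The cost is a sentence or two of text, one or two residual degrees of freedom out of 14, and a variance penalty of about 8% or 18% if the covariates turn out to be unrelated to the outcome. The sample size does not change.
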